3.3 Definition of dose limiting toxicity

Some of the DLT and MTD definitions are derived from the NCI CTCAE Version 4.02. Please note that not all of the events described as DLTs are fully supported by NCI CTCAE but are formed by amalgams of different events in order to assist with assessments of AEs.

A DLT is defined as a probably or highly probably drug-related AE occurring during Cycle 1 (i.e. the first 28 days) which fulfils one or more of the following criteria, despite appropriate supportive clinical management (however, all clinically significant toxicities will be considered in dose review decisions and the determination of the Phase II dose):

- Neutropenia Grade 4 (absolute neutrophil count [ANC] < 0.5 x 10⁹/L) for ≥ seven days *see note;
- Febrile neutropenia with Grade 3 or 4 neutropenia ANC <1.0 x 10⁹/L and a single temperature of ≥ 38.3°C or a sustained temperature ≥38 °C for more than one hour);
- Clinically significant infection (documented clinically or microbiologically) with Grade 3 or 4 neutropenia (ANC <1.0 x 10⁹/L);
- Thrombocytopenia Grade 4:
 - a) for \geq five days *see note, or
 - b) associated with active bleeding, or
 - c) requiring platelet transfusion.
- Grade 3 or 4 toxicity to organs other than the bone marrow, EXCLUDING:
 - Grade 3 nausea;
 - $\circ~$ Grade 3 or 4 vomiting in patients who have not received optimal treatment with antiemetics; or
 - Grade 3 or 4 diarrhoea in patients who have not received optimal treatment with anti-diarrhoeals.
 - Transient, asymptomatic Grade 3 biochemical abnormalities if agreed by the Sponsor and the Study Team, including the Chief Investigator (CI).
- Fatal event;
- Any other related toxicity which leads to discontinuation of treatment in Cycle 1, or to a delay in dosing of >7 days (excluding where the delay is >7 days due to scheduling rather than a clinical decision);
- Any other related toxicity that is greater than at baseline and is judged to be a DLT by the Sponsor, including the CI and Principal Investigators (PIs).

*Note: In the event of a Grade 4 neutropenia or Grade 4 thrombocytopenia, a full blood count must be performed at least on Day 7 (neutropenia) and Day 5 (thrombocytopenia) after the onset of the event to determine if a DLT has occurred. The investigator must continue to monitor the patient closely until resolution to Grade 3 or less.

Dose limiting toxicities defined above will be considered for the purpose of dose escalation decisions; however, should cumulative toxicity become apparent this will also be taken into consideration when determining either the next dose level, the RP2D or the dose and schedule for the expansion phase.

Should any change be made to the grade or causality of an AE during the trial that may alter its DLT status, the Sponsor must be informed immediately as this may affect dose escalation decisions.

3.4 Definition of maximum tolerated dose

If one instance of DLT as defined in (Section 3.3) is observed in a cohort of three patients, up to a total of six patients will be treated at that dose level. If one out of six patients experiences a DLT, dose escalation will continue. If two or more out of up to six patients experience a DLT, dose escalation will

stop and this dose will be defined as non-tolerated. A maximum of six evaluable patients will be treated at a dose below the non-tolerated level, to define the MTD.

The MAD will be defined as the highest dose received. This will usually represent the non-tolerated dose above the MTD, but may instead represent a maximum administrable dose if the feasible volume of infusion limits dose before toxicity does.

The RP2D for the expansion phases for both once weekly and twice weekly dosing will be determined following discussion of all clinically relevant toxicity, efficacy data, and PK results data by the CI, PIs and the Sponsor's Medical Advisor. All significant toxicities will be considered in the determination of the RP2D, including all available data from all cycles and cohorts of treatment.

3.5 Patient evaluability

3.5.1 Response

All patients who meet the eligibility criteria and receive at least one full cycle of IMP or ≥66% of the planned dose exposure of BT1718 within Cycle 1 and 2, and have a baseline assessment of disease and at least one repeat disease assessment will be evaluable for response.

In the expansion cohorts, baseline MT1-MMP H-score must also meet the positivity criteria for the patient to be evaluable.

Repeat assessments after at least four weeks are required in order for a patient to be confirmed as having a complete or partial response (CR or PR). To be assigned a status of stable disease (SD), follow-up measurements must have met the SD criteria at least once and at least six weeks after the initial dose of BT1718 is given.

3.5.2 Safety

All patients who meet the eligibility criteria and receive at least one administration of BT1718 will be evaluable for safety.

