3 TRIAL DESIGN

3.1 Clinical trial objectives and endpoints

3.1.1 **Primary objectives and endpoints**

Primary objectives	Endpoints
Dose Escalation phase	
To propose a recommended Phase II dose (RP2D) for evaluation by establishing the maximum tolerated dose (MTD) and/or maximum administered dose (MAD), of BT1718 given in patients with advanced solid tumours, at one or more dosing schedules.	Determine a dose at which no more than one out of six patients at the same dose level experiences a probable or highly probable BT1718-related DLT.
Dose escalation and expansion phase	
To assess the safety and toxicity profile of BT1718 in patients with advanced solid tumours.	Determine the frequency and causality of each AE to BT1718 and grade severity according to NCI CTCAE Version 4.02.
	The causality of all AEs will be assessed by the Investigator.

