4.1.1 Inclusion criteria

- 1. Written (signed and dated) informed consent and be capable of co-operating with treatment and follow-up
- 2. Phase I, dose escalation phase (Stages 1 and 2):
 - Histologically or cytologically proven advanced solid tumour, refractory to conventional treatment, or for which no conventional therapy is considered appropriate by the Investigator or is declined by the patient.

Phase IIa, expansion phase:

- Histologically or cytologically proven advanced solid tumour of particular interest based on pre-clinical and clinical data, refractory to conventional treatment, or for which no conventional therapy is considered appropriate by the Investigator or is declined by the patient. Phase IIa expansion cohorts will be:
 - a. Squamous NSCLC cohort retrospective MT1-MMP testing.
 - b. Basket cohort (advanced solid tumours, excluding patients eligible for one of the other recruiting expansion cohorts) high MT1-MMP expression by IHC assay using archival tumour sample (mandatory fresh tumour samples for those patients without available archival tumour samples or additional analysis is deemed necessary). Retrospective testing may be permitted for tumour types estimated to have high MT1-MMP positivity rates as per the Laboratory manual.
 - c. Additional expansion cohort(s) of squamous oesophageal cancer if confirmed as recruiting by the Sponsor (see Section 3.2).
- At least one measurable lesion according to RECIST Version 1.1, that has had objective progression on or after the last therapy

- 3. Life expectancy of at least 12 weeks
- 4. World Health Organisation (WHO) performance status of 0 1 (Appendix 1)
- 5. Haematological and biochemical indices within the ranges shown below. These measurements should be performed to confirm the patient's eligibility.

Laboratory Test	Value required
Haemoglobin (Hb)	≥90.0 g/L, or ≥100.0 g/L if transfusion within last four weeks
Absolute neutrophil count (ANC)	≥1.5 x 10 ⁹ /L
Platelet count	≥100 x 10 ⁹ /L
Bilirubin	≤1.5 x upper limit of normal (ULN) NB: >1.5 x ULN, acceptable if conjugated bilirubin is ≤1.5 x ULN

Alanine amino-transferase (ALT), aspartate amino-transferase (AST) and alkaline phosphatase (ALP)	≤2.5 x ULN (or ≤5 x ULN if has liver metastases)
Renal function	
Either:	
Serum creatinine	≤1.5 x ULN
Or:	
Calculated creatinine clearance (using the Wright or Cockcroft & Gault [C&G] formula)	GFR ≥50 mL/min (uncorrected value)
Or:	

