7.5.2 Phase I, stage 2 and Phase IIa, (once weekly dosing)

Observation/ Investigation	Pre screening	Pre treatme evaluations period)	ent s (screening	Cycle 1			Cycle 2 onwards	Off study	Follow-up	Survival Follow-up	
	6 months to Day-7 (Expansion phase only)	Within 28 days (Day -28 to Pre dose Day 1)	Within 8 days before study inclusion	Day 1	Day 8	Day 15	Day 22	Days 1, 8 and 15	Off study: (28 ±7 days after last dose of IMP)	At least monthly	Until end of trial
Bloods for haematology and biochemistry (e) (f)			X	Х	Х	X	Х	X	X		
Coagulation tests (g)			X								
Renal function			Х								
Urinalysis			x	Х			Х	X (Day 1 only)	Х		
Glucose finger-prick test before and after BT1718 administration (diabetic patients only) (h)				x	x	X		X			
Electrocardiogram (ECG) (i)			X	Х				X (Day 1 only)	Х		
BT1718 administration (+/- 1 day)				Х	Х	Х		X			
Temperature, blood pressure (seated or lying after 5 mins rest) and pulse (r)			X	Х	X	X	X	X	X		
WHO performance status			X	Х	Х	X	Х	х	X		

Observation/ Investigation	Pre screening	Pre treatme evaluations period)	ent s (screening		Cycle 1				Off study	Follow-up	Survival Follow-up
	6 months to Day-7 (Expansion phase only)	Within 28 days (Day -28 to Pre dose Day 1)	Within 8 days before study inclusion	Day 1	Day 8	Day 15	Day 22	Days 1, 8 and 15	Off study: (28 ±7 days after last dose of IMP)	At least monthly	Until end of trial
Blood for PK (k)				Refer	to Lab r	nanual fo	or exact t	timings			
Follow-up contact for survival/ progression (n)											X (n)

- (a) Archival sample if available in Phase I, the dose escalation phase (retrospective MT1-MMP status). Tumour sample, whether archival or fresh, mandatory in Phase IIa, the expansion phase to confirm patient eligibility (retrospective testing for tumour types estimated to have high MT1-MMP positivity rates, as per the Laboratory manual). Archival tumour biopsy sample can be obtained within six months prior to the first dose. Fresh screening tumour biopsy/standard of care biopsy must be performed/obtained within eight weeks prior to first dose.
- (b) **Pregnancy test**: For female patients of child-bearing potential.
- (c) Complete physical examination to be performed Pre treatment then all subsequent examinations can be symptom-directed and only performed as clinically indicated
- (d) Screening **weight** can be used to calculate BSA for Cycle 1.

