9.5 Recording of adverse events and serious adverse events in eCRFs

All AEs, including SAEs, must be recorded in the eCRF for eligible patients. All concomitant medications, including herbal medications and supplements must be recorded. Any therapy used to treat the event must be recorded. The eCRF will be reconciled with the safety database during and at the end of the trial. Therefore, the sites should ensure the data entered on the paper SAE report form (which is used by the Pharmacovigilance Department only) and the data entered into the eCRF are consistent. The Sponsor's Medical Advisor and the Investigator(s) will regularly review the safety database.

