13.2 Presentation of data

Data will be presented in a descriptive fashion. Variables will be analysed to determine whether the criteria for the trial conduct are met. This will include a description of patients who did not meet all the eligibility criteria, an assessment of protocol deviations, IMP accountability and other data that impact on the general conduct of the trial.

Baseline characteristics will be summarised for all enrolled patients. Patients who died or withdrew before treatment started or did not complete the required safety observations will be described and evaluated separately.

Treatment administration will be described for all cycles. Dose administration, dose modifications or delays and the duration of therapy will be described.

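### The safety set in section 3.5.2 requires eligibility as well as dosing, so a dosed patient later found ineligible falls out of the primary safety analysis

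*Protocol*

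**What the plan says.** Safety is a primary objective in both escalation and expansion (section 3.1.1): "To assess the safety and toxicity profile of BT1718 in patients with advanced solid tumours". Its endpoint is to "Determine the frequency and causality of each AE to BT1718 and grade severity according to NCI CTCAE Version 4.02".

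The set for that endpoint is defined in section 3.5.2: "All patients who meet the eligibility criteria and receive at least one administration of BT1718 will be evaluable for safety".

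Other sections bear on it:

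- Section 13.2 expects that some enrolled patients will not have met every criterion and says they will be described. It also says: "Patients who died or withdrew before treatment started or did not complete the required safety observations will be described and evaluated separately".
- Section 13.3 plans descriptive adverse event tables by dose level and names no analysis set.
- Section 9.5 says: "All AEs, including SAEs, must be recorded in the eCRF for eligible patients".
- The closing note of section 7.1.3 requires all adverse events to be recorded in the eCRF from consent, with no eligibility limit.
- In the expansion phase, inclusion criterion 2 (section 4.1.1) lists "Squamous NSCLC cohort retrospective MT1-MMP testing" for the lung cohort. For the basket cohort it adds: "Retrospective testing may be permitted for tumour types estimated to have high MT1-MMP positivity rates as per the Laboratory manual". Footnote (a) to the schedule in section 7.5.2 calls the tumour sample "mandatory in Phase IIa, the expansion phase to confirm patient eligibility".
- Section 3.5.1 makes MT1-MMP positivity a further condition for evaluability, under the heading of response.

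**The concern.** The usual safety population in an early-phase oncology trial is everyone who received the drug, because toxicity follows from exposure and not from whether the entry checks were correct. Section 3.5.2 adds a second gate. A patient dosed despite, say, an organ-function or cardiac breach that comes to light later has been exposed and may have had adverse events, yet by the written definition is not evaluable for safety.

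Two things are at stake. One is a fixed and complete denominator for a primary endpoint. The other is the information in each exposed patient, which matters when the planned cohorts hold about 16 evaluable patients. Retrospective MT1-MMP testing adds a question specific to this trial: if a low result counts as an eligibility failure, patients could leave the safety set because of a laboratory result that arrives after treatment has begun.

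**Working it through.** **Does any section restore a dosed but ineligible patient?**

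1. Section 3.5.2 joins the two conditions with *and*; failing either one removes the patient.
2. Section 13.2 summarises baseline characteristics for all *enrolled* patients and separately foresees enrolled patients who failed a criterion. The protocol therefore distinguishes enrolled from eligible, and section 3.5.2 uses the narrower group.
3. Section 13.3 gives no set of its own, so section 3.5.2 is the only definition available.
4. Section 3.4 brings all available toxicity data into the choice of the RP2D. That governs a dose decision and does not define the set for the safety analysis.

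Nothing restores the patient.

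**Does a low MT1-MMP result make a patient ineligible?**

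- *Suggesting yes:* testing is listed inside inclusion criterion 2, and footnote (a) in section 7.5.2 links the sample to confirming eligibility and, in the same sentence, allows retrospective testing.
- *Suggesting no:* criterion 2a names retrospective testing but sets no threshold for squamous NSCLC. Section 3.5.1 treats positivity as additional to eligibility, and section 13.6 ties it to the anti-tumour objective. Section 5.6.1.2 replaces such patients without removing them from safety.

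The balance favours their staying in the safety set, but the text does not settle it.

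**What does dropping dosed patients cost?**

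The protocol states no figure for the safety set, so there is none to reproduce. Assume 16 patients kept in a cohort (the section 13.1 target, used here only as a convenient size) and *m* dosed patients dropped. The value of *m* is not in the protocol; 0 to 8 is assumed. With n = 16 + m dosed patients:

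- share dropped = m / n
- probability of seeing at least one case of an event with true rate 5% = 1 − 0.95^n
- exact (Clopper-Pearson) upper 95% limit with zero events = 1 − 0.025^(1/n)

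| m | n dosed | Share dropped | P(at least 1 case), all dosed | Upper limit, 0 events, all dosed |
|---|---|---|---|---|
| 0 | 16 | 0% | 0.560 | 20.6% |
| 2 | 18 | 11% | 0.603 | 18.5% |
| 4 | 20 | 20% | 0.642 | 16.8% |
| 8 | 24 | 33% | 0.708 | 14.2% |

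Under section 3.5.2 the analysis stays on the first row whatever *m* is. With m = 4, the probability of seeing the event is 1 − 0.95^16 = 0.560 instead of 1 − 0.95^20 = 0.642. The zero-event limit is 20.6% instead of 16.8%.

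**Which way does the rate move?**

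Suppose 2 of the 16 kept patients have an event: 2/16 = 12.5% (95% CI 1.6 to 38.3%).

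- If 2 of the 4 dropped also have it, the all-dosed rate is 4/20 = 20.0% (5.7 to 43.7%), and the reported rate is too low.
- If none of the 4 has it, the all-dosed rate is 2/20 = 10.0% (1.2 to 31.7%), and the reported rate is too high.

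**The case against.** The strongest reply is that this is loose wording with little consequence. Patients are enrolled only once confirmed eligible (section 7.1.4) and treated only after registration is confirmed (section 4.2), so dosed-but-ineligible patients should be few. Section 13.3 states no eligibility filter for the adverse event tables. Tolerability in expansion is monitored continually and formally assessed after the first six patients have had two cycles (section 5.4.4), also without a filter. Safety reporting is descriptive, so no test or threshold depends on the set. All of this limits the consequence. It does not change the definition in section 3.5.2, and section 13.2 shows that the protocol expects some such patients.

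Three stronger readings are tempting but unsupported:

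- *That adverse events of ineligible patients would not be recorded.* In section 9.3, eligible patients are the group left after pre-screening and screening failures, and section 9.5 is naturally read the same way. Section 7.1.3 requires recording from consent, section 7.2.2 requires assessment at each visit, and section 9.4 requires all SAEs to be reported. The data should exist.
- *That MT1-MMP-low patients are excluded from safety.* As shown above, positivity is stated as a condition for response only; footnote (a) leaves an ambiguity, not an exclusion.
- *That section 13.2 removes dosed patients with incomplete safety observations.* It provides for separate description and evaluation, and section 3.5.2 asks for only one administration.

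**Conclusion.** The point holds as a defect in one definition. Followed as written, section 3.5.2 leaves dosed patients who are later found ineligible out of a primary safety analysis. This is not a gap left to a statistical analysis plan: the protocol fixes the set, and an analysis plan using all treated patients would contradict it.

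The size is unknown because the number affected is not given. The loss of exposure is certain for each patient dropped: under the assumed 4 dropped beside 16 kept, a fifth of the exposed patients go. The direction of bias is not fixed, so a reader should not infer that toxicity is necessarily understated.

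Nor should a reader set the ceiling of 70 expansion patients against 3 × 16 = 48 evaluable and take the difference of 22 as lost to safety. That gap concerns the evaluable targets, and it also has to cover replacements for low exposure and possible further cohorts. None of those patients is shown to be outside the safety set. Dose selection in the completed Phase I drew on all available toxicity data and is not called into question.

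**What to change.** Reword section 3.5.2 so that dosing is the only condition, for example: *every patient given at least one dose of BT1718 is evaluable for safety, regardless of eligibility or MT1-MMP result*. The last words also remove the doubt raised by footnote (a) in section 7.5.2.

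Two further edits are clarifications only:

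- Section 9.5: align the scope of eCRF recording with the note in section 7.1.3, so that it plainly covers every dosed patient.
- Section 13.2: state that dosed patients with incomplete safety observations stay in the main adverse event tables, with any separate description being additional.

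A sensitivity table restricted to eligible patients can be kept if the sponsor wants one. The cost is a few sentences at the next amendment. No new visits or assessments are needed, since the protocol already calls for these adverse events to be collected.

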9.3.3 Eligible patients

For eligible patients, SAE and AE collection and monitoring will commence at the time the patient provides written consent to participate in the trial and will continue until 28 days after the last administration of BT1718 or until the patient starts another anti-cancer therapy.

Should an Investigator become aware of any drug-related SAEs after this 28 day period, these must also be reported to the Sponsor within the expedited timelines in Section 9.4.

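### Section 3.5.2 makes the safety set depend on meeting the eligibility criteria, so a dosed patient later found ineligible is, as written, outside a primary endpoint

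*Protocol*

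**What the plan says.** Section 3.1.1 gives, as a primary objective of both escalation and expansion, "To assess the safety and toxicity profile of BT1718 in patients with advanced solid tumours". The endpoint is the frequency, causality and CTCAE grade of adverse events.

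Section 3.5.2 defines who counts: "All patients who meet the eligibility criteria and receive at least one administration of BT1718 will be evaluable for safety". Both conditions must hold.

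Section 13.2 deals with breaches of entry criteria as a matter of trial conduct: "This will include a description of patients who did not meet all the eligibility criteria". Section 13.3 tabulates adverse events by dose level and names no analysis set.

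On MT1-MMP, inclusion criterion 2 in section 4.1.1 lists "Squamous NSCLC cohort retrospective MT1-MMP testing". For the basket cohort it asks for high expression, but adds: "Retrospective testing may be permitted for tumour types estimated to have high MT1-MMP positivity rates as per the Laboratory manual". Footnote (a) to the schedule in section 7.5.2 calls the tumour sample "mandatory in Phase IIa, the expansion phase to confirm patient eligibility (retrospective testing for tumour types estimated to have high MT1-MMP positivity rates". Sections 3.5.1 and 13.6 state MT1-MMP positivity as a condition for response evaluability.

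**The concern.** A safety set is normally defined by exposure, because a drug can harm a patient whether or not an entry criterion was met. Several criteria here screen for vulnerability: organ function, unresolved toxicity from earlier treatment, cardiac disease, high medical risk. Patients who breach one of these are plausibly at higher risk of severe events, so removing them would tend to lower the reported toxicity rate.

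Some criteria are also judgemental, such as high medical risk or any other condition that in the investigator's opinion makes the patient a poor candidate. In an open-label trial these can be re-judged once an event is known. No section describes such a step, but the wording of 3.5.2 does not prevent it.

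Retrospective MT1-MMP testing adds a second uncertainty. A biomarker result can arrive after dosing, and the protocol does not say clearly whether a low score makes the patient ineligible or only removes the patient from the response analysis.

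**Working it through.** The protocol states no figure on this point, so there is none to reproduce. The check is mainly textual, with arithmetic for scale.

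**1. Is there an all-treated set elsewhere?** Section 3.5.2 requires eligibility and dosing. Section 13.2 describes patients who did not meet the criteria but does not return them to any set. Section 13.3 names no population. Section 3.5.3 concerns dose-escalation decisions only. No section defines a safety set by exposure alone.

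**2. Could meeting the criteria mean judged eligible at registration?** Section 4.2 has eligibility determined in screening, before treatment, so this reading is possible. But 3.5.2 does not say so, and 13.2 speaks of patients who did not meet all the criteria, which treats a breach as a fact that can be established about trial patients. Footnote (a) of 7.5.2 also allows eligibility to be confirmed by retrospective testing.

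**3. Does a low H-score make a dosed patient ineligible?**
- Suggesting yes: footnote (a) of 7.5.2 ties the sample to eligibility, including where testing is retrospective. Basket criterion 2b requires high expression and allows retrospective testing for some tumour types.
- Suggesting no: section 3.5.1 adds the H-score as a further condition on top of eligibility, under response only. Section 13.6 confines positivity to the anti-tumour objective. NSCLC criterion 2a names retrospective testing but sets no expression level. Section 5.6.1.2 says low-score patients are replaced and does not call them ineligible.

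The protocol does not settle the question.

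**4. How many patients could be affected?** Inputs: up to 70 patients expected in Phase IIa (sections 1 and 3.2); about 16 evaluable in each of three named cohorts (section 13.1).
- Three cohorts: 3 × 16 = 48, and 70 − 48 = 22. Response evaluability also requires eligibility (3.5.1), so ineligible patients must lie within these 22.
- A fourth cohort of 16, which the protocol contemplates without fixing: 4 × 16 = 64, and 70 − 64 = 6.
- The 22 also include patients replaced for under-dosing, who meet the criteria and stay in the safety set. The documents do not split the gap, so the range is 0 to 22.

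**5. What would the loss do?** The chance of seeing at least one case of an event with true rate p in n patients is 1 − (1 − p)^n. With no cases seen, the one-sided 95% upper bound is 1 − 0.05^(1/n). The rates p are assumed.

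| Quantity | n = 70 (none lost) | n = 64 (6 lost) | n = 48 (22 lost) |
|---|---|---|---|
| Chance of seeing a 2% event | 75.7% | 72.6% | 62.1% |
| Chance of seeing a 3% event | 88.1% | 85.8% | 76.8% |
| Chance of seeing a 5% event | 97.2% | 96.2% | 91.5% |
| Upper bound, zero events | 4.2% | 4.6% | 6.1% |

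The n = 48 column is an extreme, not an expectation.

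**6. One patient.** If 17 patients are dosed in a cohort and one dies of toxicity, the rate is 1/17 = 5.9%. If that patient is later classed as ineligible, the safety set shows 0/16. These counts are illustrative. They show that the rule matters even when very few patients are affected.

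**The case against.** The strongest reply is that the protocol already captures and uses these data. Section 9.3 is ordered by screening outcome: pre-screening failures, screening failures, then eligible patients. So "For eligible patients, SAE and AE collection and monitoring will commence at the time the patient provides written consent" in 9.3.3, and "All AEs, including SAEs, must be recorded in the eCRF for eligible patients" in 9.5, most naturally refer to patients who passed screening, which includes everyone dosed. The note in section 7.1.3 requires all adverse events to be recorded from consent, section 7.2.2 requires assessment before each administration, and section 9.4 requires all serious events to be reported whatever their cause. Section 3.4 bases the recommended dose on all available data, and section 5.4.4 keeps expansion tolerability under continual review. Safety is summarised descriptively, so no test has an error rate that could be distorted.

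This stands as far as collection and dose decisions go. A reader might infer from 9.3.3 and 9.5 that events in dosed but ineligible patients go unrecorded; the sections above do not support that. What the reply does not do is put such a patient back into the set that 3.5.2 defines for the reported primary endpoint.

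Two other inferences go too far. One is that 22 of 70 patients (22/70 = 31%) would be lost to safety; the gap also covers under-dosed patients who remain in the set, and room for further cohorts. The other is that every squamous NSCLC patient with a low H-score drops out of safety; criterion 2a sets no expression level, and 3.5.1 and 13.6 attach positivity to response.

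**Conclusion.** The point holds for the definition of the safety set. As written, 3.5.2 can exclude an exposed patient from a primary endpoint because of an eligibility finding made after dosing, and nothing else in the protocol reverses that. It is a stated rule, so an analysis plan that follows the protocol would inherit it.

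The size is unknown. In Phase IIa it lies between 0 and at most 22 patients, assuming a total of 70 and three cohorts filled to 16. If entry breaches are rare, the effect on overall rates is small, but one severe event in one excluded patient could still change a cohort's reported profile.

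The MT1-MMP route is an ambiguity, arising from footnote (a) of 7.5.2 and basket criterion 2b. The main point does not depend on it, since a breach of any criterion has the same effect.

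**What to change.** Reword section 3.5.2 so that exposure alone defines the set, for example: the safety set comprises every patient given any BT1718, irrespective of a later finding of ineligibility or of a low or unknown MT1-MMP H-score. This also settles the H-score question for safety. Keep the section 13.2 description of ineligible patients as an additional listing.

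Sections 7.4.1, 9.3.3 and 9.5 need no change, because capture in dosed patients is already required. Aligning their wording is optional.

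The cost is one sentence, with no extra patients or procedures. Section 13 places the final analysis at the end of the trial or at early termination, so a change made before then can still govern the reported tables. The downside is that the reported toxicity rate may be slightly less favourable.
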